#### 5 year futility interim assessment

The second interim analysis will be when 50% of patients reach 5-year follow-up, using stochastic curtailment to assess futility for the primary endpoint. Conditional power (CP) will evaluate the probability of achieving a significant result at the end of the trial based on accumulated data. A pre-defined non-binding stopping boundary will be decided with the DMEC, as per FDA adaptive designs guidance (U.S. Department of Health and Human Services Food and Drug Aministration 2019). Assessing futility, assuming an estimated CP bound of 20%, will reduce overall power to  $\geq$ 87.5% while not inflating type I error (Sully *et al.* 2014).

## 13.4 Primary endpoint analysis

The number and proportion of participants completing the CTB COMP will be presented at baseline, 1, 12, 24, 36, 48 and 60 months post end of RT. The reasons for missingness will be presented where available. Summary statistics will be presented for NCF scores at each time point, including raw scores and Z-scores for each test and composite mean score, overall and by treatment arm.

A mixed effects repeated measures model will be used to assess the difference in mean NCF scores between the treatment arms. The model will adjust for the minimisation factors, baseline NCF score, time point, treatment group, and treatment group by time point interaction as fixed effects. Participant and (if appropriate) participant-time interaction will be fitted as random effects.

The difference between treatments arms will use contrasts to represent the final estimated treatment effect with associated 95% confidence intervals (CIs), and additional 96% (4% level) CIs if there is no significant effect at the interim analysis. The differences will be presented for 1, 12, 24, 36, 48 and 60 months post end of RT, however, the analysis of primacy will focus on the 60 months / 5-year treatment effect.

The effect size, accounting for standard deviation, will also be estimated in line with the sample size assumptions.

The missing data mechanism will be explored and, if appropriate, multiple imputation may be considered.

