# 11 Endpoints

# 11.1 Primary endpoint

## **Neurocognitive function**

Neurocognitive function (NCF) for the primary endpoint will be measured and assessed using the composite score of the EORTC core CTB COMP; consisting of HVLT-R, TMT-A/B and COWA. Neurocognitive assessments will be performed face-to-face on paper-based tests at baseline and 1, 12, 24, 36, 48 and 60 months post end of RT.

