# 12 Statistical Considerations

# 12.1 Sample size

The required sample size is 246 patients, recruited over 3½ years.

NCF is measured using CTB COMP, calculated from the mean of standardized z-scores for the HVLT-R, TMT-A/B, and COWA. The sample size for NCF at 5 years is based on a two-sample t-test. A Cohen's d of 0.5 is considered a moderate effect size (Cohen 1988); assuming a common standard deviation (SD) of 1 this effect size equates to a mean z-score of 0.5, and is deemed clinically relevant in this setting given that patients are typically young and of working age, so even small deteriorations will likely result in noticeable everyday issues (Giovagnoli and Boiardi 1994; Boele *et al.* 2014). This is the same targeted difference in CTB COMP score adopted in the NRG-BN005 US PBT vs. photon RT glioma study (NCT03180502) (NRG Oncology 2017). Based on a two-sample t-test with 5% two-sided significance and 90% power, 172 patients (86 per arm) are required to detect an effect size of 0.5. Assuming 30% loss to follow-up at 5 years (Cohen 1988; Klein 2019), 123 patients will be required per arm.

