# 13.5 Secondary endpoint analysis

#### Additional tests of neurocognitive function

The CNS vital signs battery tests which will form cognitive domains. Summary statistics for the raw scores and z-scores for cognitive domains will be presented, for each time point, overall and by treatment arm. Similar mixed effects repeated measures models used for the primary outcome will also be used for the additional NCF outcomes. The difference between treatment arms of each cognitive domain with associated 95% confidence intervals (CIs) will be presented for 1, 12, 24, 36, 48 and 60 months post end of RT.

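### One baseline NCF slope for all visits: the 60-month contrast loses some precision if that slope weakens over time, and can be biased if score-related dropout also differs by arm

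*Protocol*

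**What the plan says.** Section 11.1 has the primary battery performed "at baseline and 1, 12, 24, 36, 48 and 60 months post end of RT". Section 13.4 models the six post-baseline visits together. Besides the minimisation factors, the terms are "baseline NCF score, time point, treatment group, and treatment group by time point interaction as fixed effects". For the covariance, "Participant and (if appropriate) participant-time interaction will be fitted as random effects". Differences are reported at every visit, but "the analysis of primacy will focus on the 60 months / 5-year treatment effect".

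On missing data, section 12.1 sizes the trial "Assuming 30% loss to follow-up at 5 years", with no split by arm. Section 13.4 adds: "The missing data mechanism will be explored and, if appropriate, multiple imputation may be considered".

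The specification is reused. Section 13.5 says of the CNS Vital Signs battery: "Similar mixed effects repeated measures models used for the primary outcome will also be used for the additional NCF outcomes". It applies the same model to the HRQoL outcomes.

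**The concern.** A baseline main effect without a baseline-by-time term forces one regression slope on a score taken about 4 months after baseline (the wait for radiotherapy, about 6 weeks of treatment, one further month) and on one taken more than 5 years after it. If the true slope is smaller at 60 months than at the early visits, the common slope is too steep at the visit that decides the trial.

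Two things can follow:

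- **Precision.** Over-adjusting for baseline leaves avoidable residual variance in the 60-month contrast.
- **Bias.** Randomisation balances baseline between arms, so a wrong slope does no systematic harm while everyone is observed. If the patients retained in the two arms differ in mean baseline NCF, the wrong slope corrects that difference by the wrong amount. When low scorers leave the photon arm more often, the error favours PBT.

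The trial is open-label and expects 30% loss, and multiple imputation is only a possibility. The likelihood model therefore carries most of the missing-data burden and depends on a correctly specified mean.

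**Working it through.** **1. The plan's own figures reproduce.** Section 12.1: "Based on a two-sample t-test with 5% two-sided significance and 90% power, 172 patients (86 per arm) are required".

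- Normal approximation: 2 × (1.960 + 1.282)² / 0.5² = 84.1, so 85 per arm. The t-distribution gives 86.
- Dropout: 86 / 0.70 = 122.9, so 123 per arm and 246 in total.
- Power at 5 years, alpha 0.04: SE = √(2/86) = 0.1525, and Φ(0.5/0.1525 − 2.054) = 0.890 (t: 0.886). The plan says about 89%.
- Power at 2 years, alpha 0.01, 110 per arm: 0.871 (t: 0.865). The plan says about 87%.

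None of these uses the mixed model or a baseline slope.

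**2. Assumed inputs.** The protocol gives no baseline/follow-up correlation and no dropout by arm. Three baseline correlations (month 1 to month 60) were tried at constant SD: flat 0.70, moderate 0.82 to 0.50, steep 0.78 to 0.23. The model was fitted with one slope and with a slope per visit, under an unstructured covariance and under random intercept plus slope, which is closest to section 13.4.

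**3. Precision at 60 months** (N = 246, 30% loss unrelated to scores). Power = Φ(0.5/SE − 2.054).

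| Correlation | Covariance | SE, one slope | SE, slope per visit | Ratio | Power at 4% |
|---|---|---|---|---|---|
| Flat | unstructured | 0.104 | 0.104 | 1.00 | no difference |
| Moderate | unstructured | 0.1314 | 0.1264 | 1.04 | 96% vs 97% |
| Moderate | random intercept + slope | 0.1387 | 0.1336 | 1.04 | 94% vs 95% |
| Steep | unstructured | 0.1556 | 0.1441 | 1.08 | 88% vs 92% |
| Steep | random intercept + slope | 0.1672 | 0.1551 | 1.08 | 83% vs 88% |

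With a milder fall in correlation the variance rises by only about 1%, and √1.01 = 1.005. Hence the range of 0.5-8% in SE.

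**4. Bias at 60 months with one slope** (unstructured covariance, large samples). The first rate is for the arm losing more low scorers, taken as photon; the sign reverses if it is PBT.

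| Dropout pattern | Moderate | Steep |
|---|---|---|
| 40% vs 20%, unrelated to baseline | 0.000 | −0.001 |
| 30% vs 30%, low baseline, same in both arms | 0.000 | −0.001 |
| 40% vs 20%, low baseline in both arms | +0.03 | +0.05 |
| 40% low baseline vs 20% at random | +0.06 | +0.09 |
| 30% vs 30%, opposite dependence on baseline | +0.09 | +0.14 |

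With a flat slope the bias is about zero in every row. With baseline by visit it is about 0.002 or less throughout. Random intercept plus slope does not remove it: the fourth row becomes +0.056 and +0.082.

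The mechanism shows in the steep column. Retained-patient baseline differences (PBT minus photon) of −0.155, −0.296 and −0.434 go with biases of +0.0489, +0.0918 and +0.1395. The ratios are −0.32, −0.31 and −0.32, so the bias is close to proportional to the imbalance among those retained.

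**5. A more moderate pattern.** Let loss depend on the last score in the photon arm only (33% vs 27% lost), with correlation falling from about 0.8 to 0.5-0.75. The null contrast is then biased by +0.018 to +0.052, and by −0.006 to +0.002 with the interaction. Against the target, 0.02/0.5 = 4% and 0.05/0.5 = 10%. The 4% test would reject about 4.3-5.6% of the time.

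**6. Rejection under no effect** (600 trials of N = 246 per case, nominal 4%, Monte Carlo error √(0.04 × 0.96/600) = 0.8 points). In the last two rows of the bias table, one slope rejects in 6.3-10.8% of trials, against 4.7-5.3% with baseline by visit. With 40% vs 20% loss unrelated to baseline, one slope gives 5.3% and 3.8%, which is compatible with nominal.

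**The case against.** **It is detail for the analysis plan.** Section 13.1 calls the text an overview and promises a full SAP, which may add the term. That is fair, but section 13.4 names the fixed effects one by one and interacts only treatment with time. A SAP that follows it inherits the restriction.

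**A falling correlation is not a falling slope.** This stands. The slope is the correlation times the ratio of follow-up SD to baseline SD. If patients diverge at rates unrelated to their starting level, the spread grows and the slope stays constant. A correlation falling from 0.82 to 0.50 leaves the slope unchanged if the SD grows by 0.82/0.50 = 1.64 between month 1 and month 60. The common-slope model is then correct. A reader might infer that the slope is certainly too steep at 60 months; the protocol gives nothing that shows it.

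**Differential dropout alone does no harm.** This stands too. A reader might infer that any difference in loss between arms biases the contrast. The first row of the bias table shows that it does not. Both a changing slope and a difference in baseline NCF among retained patients are needed, and the protocol predicts neither. Section 9.8 also keeps patients in cognitive testing after progression, which limits one route to score-related loss.

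**Multiple imputation could repair it.** Imputing each visit from baseline and earlier scores would restore balance between the arms. The protocol only says that this may be considered, so it cannot be relied on.

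**Conclusion.** The point holds as a conditional and modest one. The listed model imposes a constant baseline slope from 1 to 60 months.

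- If the slope weakens, the 60-month SE is about 0.5-8% larger than it need be; if the slope is constant, nothing is lost.
- If score-related dropout also leaves the arms with different baseline NCF, the contrast can be biased by about 0.02-0.05 SD under moderate patterns, and by up to 0.14 SD under the stronger patterns tabulated.

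All of these sizes rest on assumed correlations and dropout patterns.

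A reader might also infer that the trial is underpowered. The documents do not support that: the stated sample size and power come from an unadjusted t-test and reproduce. With an unstructured covariance, the one-slope model still gives 88-96% in the cases where the slope falls. Only the steepest assumed decline combined with random slopes falls clearly below the stated figure (83%).

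**What to change.** In section 13.4, add a baseline NCF score by time point interaction to the fixed effects. Carry the same term into the CNS Vital Signs and HRQoL models in section 13.5, each with its own baseline score.

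The cost is five extra parameters in the primary and CNS Vital Signs models (six post-baseline visits, less one). For HRQoL it is eight if all nine post-baseline assessments enter the model. No further data are needed, and practically nothing is lost if the slope proves constant (SE 0.104 either way). The change should be made in the protocol or SAP before any analysis by arm.

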# 13.5 Secondary endpoint analysis

#### Additional tests of neurocognitive function

The CNS vital signs battery tests which will form cognitive domains. Summary statistics for the raw scores and z-scores for cognitive domains will be presented, for each time point, overall and by treatment arm. Similar mixed effects repeated measures models used for the primary outcome will also be used for the additional NCF outcomes. The difference between treatment arms of each cognitive domain with associated 95% confidence intervals (CIs) will be presented for 1, 12, 24, 36, 48 and 60 months post end of RT.

#### Health Related Quality of Life (HRQoL)

Questionnaires will be scored using respective scoring manuals. Summary statistics will be presented overall and by treatment arm for the HRQoL questionnaires including all the domains for the EORTC QLQ-C30 and EORTC BN20 module, the EQ-5D-5L, MFI and HADS scores. Change in mean score from baseline with 95% CIs will also be reported. Summaries will be presented for each treatment group and overall, at each follow-up time point.
The same mixed effects repeated measures model used for the primary outcome will also be used for HRQoL outcomes.

#### Endocrinopathy

Summary statistics will be presented for each specific endocrinopathy overall and by treatment arm. This will include: growth hormone deficiency, cortisol deficiency, secondary hypothyroidism, gonadotrophin deficiency in males, gonadotrophin deficiency in pre- and post-menopausal women and prolactin abnormalities. The need for any endocrine replacement or blocking therapies will also be presented using summary statistics.

### Treatment compliance

Summary statistics will be presented by treatment arm for the total dose of radiotherapy received and the duration of treatment. Number of participants withdrawing from treatment and reasons for interruption to PBT or photon radiotherapy schedules or for PBT patients needing to receive fractions of photon radiotherapy will be summarised. The number of chemotherapy cycles received, doses, the proportion of participants experiencing modifications and associated reasons will be reported. The effect of radiotherapy dose and type (i.e. photon RT or PBT) on chemotherapy compliance will be explored.

#### Work and economic impact

Summary statistics of the participant and caregiver WPAI:GH scores will be presented overall and by treatment arm for each of the follow-up time points. Each of the four types of scores will be calculated and summarised for:

- Absenteeism (work time missed)
- Presenteeism (impairment at work / reduced on-the-job effectiveness)
- Work productivity loss (overall work impairment / absenteeism plus presenteeism)
- Activity Impairment

The additional health utilisation data will be presented with summary statistics. Additional analysis of cost effectiveness may be explored, however, this will be funded by a separate grant and proposal.

#### **Caregiver distress**

The number and proportion of caregivers completing the 30-item Caregiver Needs Screen will be presented for each follow-up time point. Summary statistics of the scores will also be presented overall and by treatment arm for each follow-up time point.

#### Early and late toxicity

Summary statistics of safety data on ARs/SARs/RUSAEs experienced will be presented overall and by treatment arm for the acute and late toxicity period. The number and proportion of participants experiencing each CTCAE grade of acute and late toxicities will be summarised.

The long-term collection of clinician recorded toxicities will capture a level of symptom burden as a result of treatment. CTCAE grades of patients over time will be assessed to explore the time dependence of ARs in a population that can often experience chronic conditions. Additionally, this longitudinal data will be explored in relation to other endpoints over time e.g. HRQoL.

Safety monitoring of reactions to chemotherapy will be included and as such will be reported under the toxicity secondary objective, however, there is no hypothesis of expected differences and no plan for formal comparisons – this is being used to inform the safety of

the radiotherapy comparison. These events are collected for monitoring purposes, and completeness of symptom reporting for this patient population across the course of the trial.

#### **Radiological response rates**

Summary statistics will be presented for the proportion of participants within each clinical response status, as assessed by the RANO criteria, at baseline, 12, 24, 36, 48 and 60 months post end of RT.

#### **Progression-free survival (PFS)**

The proportion of participants who have progressed or died at 60 months postrandomisation will be reported along with 95% CIs. PFS will be presented using Kaplan-Meier (KM) curves. The median PFS estimates and 95% CIs will be presented along with the log-rank test statistic (and associated p-value) which tests for a difference in the median PFS. PFS at 60 months post-randomisation will be compared between the treatment arms using Cox's Proportional Hazards (PH) model, adjusting for the minimisation factors. The hazard ratio (HR) for the experimental arm versus the control arm (where a HR < 1 would indicate the experimental arm is better than the control) will be presented along with 95% CIs and associated p-value testing for the difference between the arms.

Participants who have not progressed/died at the time of analysis, including those lost to follow-up, will be censored at the last date they were known to be alive and progression-free. Participants who withdraw consent for data collection will be censored at the date of withdrawal if they have not progressed/died by this date.

The assumptions of the Cox PH model will be tested.

#### Overall survival (OS)

The proportion of participants who have died at 60 months post-randomisation will be reported along with 95% CIs. OS will be presented using Kaplan-Meier (KM) curves. The median OS estimates and 95% CIs will be presented along with the log-rank test statistic (and associated p-value) which tests for a difference in the median OS. OS at 60 months post-randomisation will be compared between the treatment arms using Cox's PH model, adjusting for the minimisation factors. The HR for the experimental arm versus the control arm (where a HR < 1 would indicate the experimental arm is better than the control) will be presented along with 95% CIs and associated p-value testing for the difference between the arms.

Participants who are still alive at the time of analysis, including those lost to follow-up, will be censored at the last date they were known to be alive. Participants who withdraw consent for data collection will be censored at the date of withdrawal if they have not died by this date.

The assumptions of the Cox PH model will be tested.

## 14 Trial Monitoring

Participating sites and PIs must agree to allow trial-related on-site monitoring, Sponsor audits and regulatory inspections by providing direct access to source data/documents as required. Patients are informed of this in the patient information sheet and are asked to consent to their medical notes being reviewed by appropriate individuals on the Consent Form.

CTRU will determine the appropriate level and nature of monitoring required for the trial. Risk will be assessed on an ongoing basis and adjustments made accordingly.

# 14.1 The Trial Steering Committee (TSC) and the Data Monitoring and Research Ethics Committee

The trial will be overseen by an independent TSC & DMEC.

The DMEC will monitor the trial data, safety including SARs and RUSAEs, treatment related mortalities and the associated ethics of the trial. Listings of SARs, and RUSAEs will be provided to the DMEC on a regular basis. The DMEC will be provided with detailed unblinded reports containing the information agreed in the data monitoring analysis plan, by the CTRU, at approximately 12-monthly intervals.

Trial progress will be closely monitored by the independent DMEC, who will report to the TSC, and the overall direction overseen by the TSC (ensuring regular reports to the NIHR Efficacy and Mechanism Evaluation (EME) Programme).

#### 14.2 Data monitoring

Data will be monitored for quality and completeness by the CTRU. Missing data will be chased until it is received, confirmed as not available or the trial is at analysis.

The CTRU/Sponsor will reserve the right to intermittently conduct source data verification exercises on a sample of participants, which will be carried out by staff from the CTRU/Sponsor. Source data verification will involve direct access to patient notes at the participating hospital sites and the ongoing central collection of copies of consent forms and other relevant investigation reports.

### 14.3 Clinical governance issues

To ensure responsibility and accountability for the overall quality of care received by participants during the study period, clinical governance issues pertaining to all aspects of routine management will be brought to the attention of the TSC, Sponsor and, where applicable, to individual NHS Trusts.

## 15 Quality Assurance Processes

### 15.1 Quality assurance

The trial will be conducted in accordance with the principles of GCP in clinical trials, as applicable under UK regulations, the UK Policy Framework for Health and Social Care Research and Scottish Executive Health Department Research Governance Framework for Health and Social Care 2006, and through adherence to CTRU SOPs.

## 15.2 Serious breaches

The CTRU and Sponsor have systems in place to ensure that serious breaches of GCP or the trial protocol are picked up and reported. Investigators are required to **immediately** notify the CTRU of a serious breach (as defined in the latest version of the HRA SOP) that they become aware of. A 'serious breach' is defined as a breach of the protocol or of the conditions or principles of GCP (or equivalent standards for conduct of non-CTIMPs) which is likely to affect to a significant degree-

- a) the safety or physical or mental integrity of the trial subjects, or
- b) the scientific value of the research

In the event of doubt or for further information, the Investigator should contact the Senior Trial Manager at the CTRU.

## 16 Ethical Considerations

The trial will be performed in accordance with the recommendations guiding physicians in biomedical research involving human subjects adopted by the 64th WMA General Assembly, Fortaleza, Brazil, October 2013. Informed written consent will be obtained from the participants prior to randomisation into the study. The right of a participant to refuse participation without giving reasons must be respected. The participant must remain free to withdraw at any time from the study without giving reasons and without prejudicing his/her further treatment.

